## Laboratory outcomes

### Source of information:

In the voluntary subgroup of participants whose parent consented to blood tests, blood will be collected at 6 months, 9 months, and 24 months of age to perform in-vitro stimulation assays, immune cell evaluation and vaccine responses. Just after collection, the blood will be transported to [name] laboratory at the Centre for Vaccinology of the University of Geneva, which is geographically very close and in which the assays are established. The time points will enable us to evaluate how the immune system matures and, thanks to the control group, distinguish age-induced effects from the vaccine-induced early effects.

## 9.2.1 Assessment of primary outcome

### Stage A

#### AIM1: Respiratory infections between 6 months and 9 months of age.

*Outcome measure:* Incidence of parent-reported respiratory infections between 6 months and 9 months of age using fortnightly REDCap questionnaires, with validation of data by confirmation with treating paediatrician and medical records.

## 9.2.2 Assessment of secondary outcomes

### Clinical outcomes

#### Stages A and B

#### AIM1&3: Infections

*Outcome measure:* Additional measures of infection, with measurement of the following events: any infection, otitis, upper respiratory tract infection, lower respiratory tract infection, gastroenteritis, urinary tract infection, osteoarticular infection, and trauma/accident (the latter being used as control event), including:

- (i) **Time to first event** – Calculated as:  
For participants who have an event:  
*Date of event onset - date of randomisation*  
For participants who did not have an event:  
*Earliest censoring date - date of randomisation*
- (ii) **Prevalence** - Calculated as:  
*number of participants who have an event / total number of participants*
- (iii) **Incidence** - Calculated as:  
*number of events / total time of follow-up*
- (iv) **Days free of event** - Calculated as:  
*number of days free of event / total days of follow-up of participants*
- (v) **Severity of event** – measured as:
  1. **Duration** – Per event, calculated as: *date of recovery - date of onset*
  2. **Antibiotic use** - Per event, including: *yes/no, antibiotic name, dose, route, duration*
  3. **Hospitalisation** - Per event, including: *yes/no, ward/critical care, duration, treatment received*
  4. **Outcome** - Per event, including: *uneventful/complication/sequel/death*

of each category of event, measured between 6 months and 24 months of life, using fortnightly REDCap questionnaires, with validation of data by confirmation with treating paediatrician and medical records.

#### AIMS2&4: Allergic and atopic diseases

*Outcome measure:* Occurrence and flare of eczema, food allergy, and wheezing diseases (defined as mentioned in table 4) measured as:

- (i) **Time to first event** – Calculated as:  
For participants who have a flare:  
*Date of event onset - date of randomisation*  
For participants who did not have a flare:  
*Earliest censoring date - date of randomisation*
- (ii) **Prevalence** - Calculated as:  
*number of participants who have a flare / total number of participants*
- (iii) **Incidence** - Calculated as:  
*number of flares / total time of follow-up*

- (iv) **Days free of flare** - Calculated as:  
*number of days free of flare / total days of follow-up of participants*
- (v) **Severity of flare** – measured using:
1. **Scores** – e.g. *POEM* and *SCORAD* (see table 4)
  2. **Treatment use** - Per flare, including: *yes/no, treatment name, dose, route, duration*
  3. **Hospitalisation** - Per flare, including: *yes/no, ward/critical care, duration*
  4. **Outcome** - Per flare, including: *uneventful/complication/sequel/death*
  5. **Impact on growth** – Calculated using: *evolution of biometric percentile*
  6. **Impact on quality of life** – Calculated using scores, e.g. items from *POEM* and *SCORAD*

of each event/flare, measured between 6 months and 24 months of life, using fortnightly REDCap questionnaires, with validation of data by confirmation with treating paediatrician and medical records.

**AIMS5: Influence of interventions, children, maternal and environmental factors on study outcomes**

*Outcome measure:* as defined above. Factorial and multivariate analyses will assess the impact of interventions (early MMR, non-concomitant MMR), host factors (e.g. sex, ethnicity), exposure (e.g. day-care, siblings, pets, smoking), underlying immunity (e.g. previous infections), and familial history (e.g. allergy) on the clinical outcomes defined above.

**Laboratory outcomes**

**AIM6: Immune cell sub-populations and responsiveness over time**

*Outcome measure:* Bloods will be collected at 6 months, 9 months, and 24 months of age and in-vitro whole blood stimulation will be done with unrelated pathogens and Toll-like receptor (TLR) agonists, such as:

Unrelated pathogens	TLR-agonists		
Staphylococcal aureus	TLR2/4 agonist	PEPG	Peptidoglycan
Streptococcus pneumoniae	TLR3 agonist	Poly(I:C)	Polyinosinic-polycytidylic acid
Escherichia coli	TLR4 agonist	LPS	Lipopolysaccharide
Candida albicans	TLR7/8 agonist	R848	Resiquimod
Respiratory syncytial virus (RSV)			

Table 5: Example of unrelated pathogens and Toll-like receptor (TLR) agonists used for stimulations.

The assay strip for stimulation will be made in batches, to maximise standardisation of the stimulant volume, and stored at -80°C until the addition of blood. Cytokine secretion and immune cell activation will be measured in stimulated samples using the following procedures:

**Cytokine secretion:** Whole blood diluted 1:1 in RPMI will be incubated together with either a heat-killed pathogen, a TLR-agonist or media alone. Cytokine expression will be quantified in supernatants by multiplex assays through measurement of cytokines concentrations (e.g. IFN-γ, IFN-α/β, IP-10, IL-1β, IL-4, IL-6, IL-8, IL-10, IL-12p40, MCP-1, MIG, MIP-1β, and TNF-α) in response to the in-vitro stimulation.

**Intracellular cytokine staining (ICS) assays:** Whole blood diluted 1:1 in RPMI will be cultured in the stimulation strips described in the presence of cytokine secretion inhibitors for the last 6 hours. Innate and adaptive immune cell (e.g. monocytes subsets, dendritic cell subsets, neutrophils, NK cells, NK T cells, T cells and B cells) activation and cytokine production (e.g. IFN-γ, IP-10, IL-1β, IL-4, IL-6, IL-10, IL-12p40, IL-17, IL-22 and TNF-α) will be assessed by ICS and flow/spectral cytometry as previously described.

**AIM7: Transcriptional responses and epigenetic imprinting in immune cells**

*Outcome measure:* (e.g. monocytes) in bloods collected at 6 months, 9 months, and 24 months of age, identifying functional pathways that are impacted by MMR and that might contribute to the clinical non-specific effects observed.

In brief, PBMC and granulocytes will be isolated from peripheral blood samples collect at 6 months, 9 months, and 24 months of age using a density gradient. Monocytes (or other relevant immune cell subsets identified in AIM 6) will be isolated by fluorescence activated cell sorting (FACS, cell sorter) and

analysed by transcriptomic and epigenetic analysis, to identify immune and cellular pathways that have been altered by MMR vaccination.

**Transcriptomic signatures:** Purified immune cell populations from a minimum of 20 paired samples (i.e. sample taken at 6 months, 9 months, and 24 months of age of 20 individuals) per group of primary outcome analysis (20 in Group M.C. or M.M., and 20 in Group C.M. or C.C.; see section 11.2) will be stimulated with an unrelated pathogen or media alone (Table 5). The choice of stimulation will be informed by the findings from AIM 6 (i.e. those inducing the most differences between the two groups). RNA will be isolated and RNA sequencing (RNA-Seq) will be done and mapped. Differentially expressed genes (DEGs) will be compared between groups and time points.

**Epigenetic reprogramming:** DNA will be isolated from a minimum of 20 paired purified immune cell populations samples per group (as defined above), and measure DNA methylation will be measured. Analysis of differential methylation will be done and methylation sites will be allocated to nearby genes. This will be done in similar cells and samples as for the transcriptomic analysis so both results could be correlated.

**Pathway and integration analysis:** Pathway analysis of transcriptomic and epigenomic data will be done using standard ontological analysis software. Dynamic gene promoters and distal regions with DNA methylation changes will be scanned for transcription factor motif enrichment.

#### **AIM8: Vaccine responses and memory cells**

*Outcome measure:* quantification of vaccine-specific immunoglobulin and immune cells, including memory cells at 24 months of age, compared to pre-vaccination (at 6 months or 9 months of age, depending on the group) and between groups. In order to increase the numbers for the 24-months-old between groups comparison, the 24 months blood sample will be proposed to all 500 participants, regardless of the Part, but is of course optional.

#### **AIM9: Influence of interventions, children, maternal and environmental factors on laboratory outcomes**

*Outcome measure:* as defined above. Factorial and multivariate analyses will assess the impact of interventions (early MMR, non-concomitant MMR), host factors (e.g. sex, ethnicity), exposure (e.g. day-care, siblings, pets, smoking), underlying immunity (e.g. previous infections), and familial history (e.g. allergy) on the laboratory outcomes defined above.

### **9.2.3 Assessment of other outcomes of interest**

Exploratory outcome measures may be examined, pending additional funding.

### **9.2.4 Assessment of safety outcomes**

**AIM10: Vaccine safety:** occurrence and severity of local and systemic adverse events, as well as any serious adverse events, by systemic organ class, preferred term, severity using standard grading scales (Table 6), and relationship to the intervention from day 0 to day 42 post MMR (see section 10)

Parents will be asked to fill down a 42-day vaccine diary to record adverse events including local reaction (pain, redness, tenderness, and swelling) and systemic reaction (fever, fatigue, irritability, vomiting, diarrhoea, myalgia, arthralgia, conjunctivitis, skin rash, and parotitis). Investigators will also record solicited and unsolicited events at study visits and will check with the treating paediatrician and the medical record.

	Grade 0 None	Grade 1 Mild	Grade 2 Moderate	Grade 3 Severe	Grade 4 Potentially life threatening
Local reaction					
Pain	None	Does not interfere with activity	Repeated use of nonnarcotic pain reliever > 24 hours or interferes with activity	Any use of narcotic pain reliever or prevents daily activity	Emergency room visit or hospitalisation
Redness	None	1a: < 2.5 cm 1b: 2.5 - 5 cm	5.1 - 10 cm	>10 cm	Necrosis or exfoliative dermatitis
Tenderness	None	Mild discomfort to touch	Discomfort with movement	Significant discomfort at rest	Emergency room visit or hospitalisation
Swelling / induration	None	1a: < 2.5 cm 1b: 2.5 - 5 cm and does not interfere with activity	5.1 - 10 cm or interferes with activity	>10 cm or prevents daily activity	Necrosis
Systemic (general) reaction					
Fever	None	38.0°C to 38.4°C	38.5°C to 38.9°C	39.0°C to 40.0°C	>40.0°C
Fatigue	None	No interference with activity	Some interference with activity	Significant; prevents daily activity	Emergency room visit or hospitalisation
Irritability	None	No interference with activity	Some interference with activity	Significant; prevents daily activity	Emergency room visit or hospitalisation
Nausea / vomiting	None	No interference with activity, or 1-2 episodes/24 hours	Some interference with activity or >2 episodes/24 hours	Prevents daily activity, requires outpatient IV hydration	Emergency room visit or hospitalisation for hypotensive shock
Diarrhoea	None	2-3 loose stools or < 400 g/24 hours	4-5 stools or 400-800 g/24 hours	≥6 watery stools or >800 g/24 hours or requires outpatient IV hydration	Emergency room visit or hospitalisation
Myalgia / arthralgia	None	No interference with activity	Some interference with activity	Significant; prevents daily activity	Emergency room visit or hospitalisation
Conjunctivitis	None	No interference with activity	Some interference with activity	Significant; prevents daily activity	Emergency room visit or hospitalisation
Skin rash	None	No interference with activity	Some interference with activity	Significant; prevents daily activity	Emergency room visit or hospitalisation
Parotitis	None	No interference with activity	Some interference with activity	Significant; prevents daily activity	Emergency room visit or hospitalisation

Table 6: Toxicity grading of adverse event following vaccination, according to the Food and Drug Administration. (2007). "Guidance for Industry: toxicity grading scale for healthy adult and adolescent volunteers enrolled in preventive vaccine clinical" Retrieved 20.12.2021, from

<https://www.fda.gov/downloads/BiologicsBloodVaccines/GuidanceComplianceRegulatoryInformation/Guidances/Vaccines/ucm091977.pdf>

#### 9.2.4.1 Adverse events

All adverse events, both solicited and unsolicited, will be recorded through day 42 after vaccination. For each adverse event, date and time of onset, duration, resolution, action taken, assessment of intensity/severity (Table 6) and relationship with study treatment will be recorded in REDCap.

Solicited adverse events, will be collected through day 42. They include the following:

#### 9.2.4.1.1 *Solicited local adverse event*

- Pain
- Redness
- Tenderness
- Swelling / induration

#### 9.2.4.1.2 *Solicited systemic (general) adverse event*

- Fever
- Fatigue
- Irritability
- Nausea / vomiting
- Diarrhea
- Myalgia / arthralgia
- Conjunctivitis
- Skin rash
- Parotitis

#### 9.2.4.1.3 *Unsolicited adverse event*

Unsolicited adverse events will be recorded during study visits, and through consulting with the treating paediatrician and the medical record, or if the subject's parent spontaneously contact the investigator.

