## 9. STUDY ASSESSMENTS

### 9.1 Study flow chart(s) / table of study procedures and assessments

Visit number	V1		V2		V3 a		V4	
Time point	t 0	t 0 to t +3m	t +3m	t +3m to t +6m	t +6m	t +7m	t +6m to t +18m	t +18m
Age of participant	6mo	6mo to 9mo	9mo	9mo to 12mo	12mo	13mo	12mo to 24mo	24mo
Allowed time frame	±2w	±1w	±2w	±1w	±2w	±2w	±1w	±4w
Recruitment								
Screening, eligibility check	X							
Inclusion and randomisation	X							
Baseline questionnaire b	X							
Intervention: MMR vaccination								
- Group C.C.			X		X			
- Group M.C.	X				X			
- Group C.M.			X			X		
- Group M.M.	X					X		
Assessments								
Clinical assessment c	X		X		X			X
Fortnightly questionnaire		X...X...X...X d		X...X...X...X e			X...X...X...X e	
Vaccine diary (S/AE)		X f		X f			X f	
Contact with treating paediatrician	X		X		X			X
Health record check	X		X					X
Blood collection (Part 2 only)	X		X					X

C: current schedule; MMR: measles-mumps-rubella vaccination; M: modified schedule; m: month; mo: month-old; S/AE: (serious) adverse event; V: visit; w: week.

a Timing of V3 differs between groups: 13 mo for Group M.M. and Group C.M., and 12 mo for Group M.C and Group C.C. If funding is insufficient, V3 might be simplified and delegated to the treating paediatrician.

b Includes demographics, medical history.

c Includes physical examination and eczema assessment using SCORAD.

d every 2 weeks.

e every month.

f follow-up 42 days after vaccination.

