### 9.3.2 Visit 1: Baseline and randomisation, 6 months of age ( $t_0 \pm 2$ weeks)

**Eligibility check** by investigators, with review of past medical history and of vaccination records, re-evaluation of inclusion and exclusion criteria.

**Target clinical examination** will be performed if needed, to ensure that there is no temporary exclusion criteria (e.g. if the child is sick, the inclusion can be delayed a few days until the illness resolves).

**Overview of the trial** by investigators, using the study flow chart and the participant informed consent form. Correct comprehension of the trial will be checked, with the possibility for parents to ask any remaining question.

**Blood collection will be discussed** in further details for interested parents.

**Further information** will be given to all parents, including that

- The treating physician of their child will be contacted to inform about the trial, corroborate their child's medical history and seek additional information.
- Authorised individuals other than their treating physician may examine their child's medical records.
- The blood samples taken as part of the study will be coded and stored for a period of maximum 15 years; this duration has been chosen given the likelihood that progress in the nascent field of non-specific effects of vaccines may benefit substantially from the reanalysis of study samples. Upon the approval of the Sponsor, samples may be sent outside of Switzerland to collaborating research laboratories for non-commercial research purposes.
- There is no compensation for participating in the trial.
- They are free to withdraw at any time. Unless they specifically request complete consent withdrawal, the long-term data collection, including access to medical records, will continue, in order to avoid bias as much as possible.

**Informed consent** will be sought, once the subject's parent confirm understanding and voluntarily agreeing in participating; the parent and the investigator will both date and sign the consent form.

**Inclusion in the trial**, the parent is given a copy of the signed document; the original copy is securely filed in the study documentation.

**Baseline questionnaire** will be filled down by the subject parents and reviewed with the investigator. It includes questions on demographics, medical history, and exposure, as detailed in Table 4 in section 9.2.

**Eczema assessment** will be performed, using *SCORAD* score.

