## 10.1.1 Definition and assessment of (serious) adverse events and other safety related events

### 10.1.1.1 Definition of adverse event

An **Adverse Event (AE)** is any untoward medical occurrence in a patient or a clinical investigation participant administered a pharmaceutical product and which does not necessarily have a causal relationship with the study procedure. An AE can therefore be any unfavourable and unintended sign (including an abnormal laboratory finding), symptom, or disease temporally associated with the use of a medicinal (investigational) product, whether or not related to the medicinal (investigational) product. [ICH E6 1.2]

For the period of vaccination to 42 days post vaccination only, the following solicited adverse events are non-serious adverse events of interest for this study; they will be collected using vaccine diary.

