#### 10.1.1.1.3 Unsolicited adverse events

Unsolicited adverse events will be recorded during study visits, and through consulting with the treating paediatrician and the medical record, or if the subject's parent spontaneously contact the investigator. They are defined as an adverse event of interest and will be reported as such only if they began within the first 42 days following the intervention and if the causality assessment deems the event to be possibly, probably or definitely associated to the intervention.

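### After the second MMR no scheduled contact asks about unsolicited adverse events until 24 months, some 10 months after the 42-day window closes

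*Protocol*

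**What the plan says.** Section 9.2.4.1 sets the requirement: "All adverse events, both solicited and unsolicited, will be recorded through day 42 after vaccination". For each event it asks for the date and time of onset, duration, resolution, intensity and relationship to the vaccine. Section 10.1.1.1.3 then counts an unsolicited event as one of interest only when its onset falls inside the 42 days and its link to the vaccine is judged at least possible. Section 11.4.5 tabulates day of onset, duration and causality.

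The routes of collection for unsolicited events are the same in Sections 9.2.4.1.3 and 10.1.1.1.3: "Unsolicited adverse events will be recorded during study visits, and through consulting with the treating paediatrician and the medical record". Both sections add a third route, a parent who gets in touch with the investigator unprompted.

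On the diary, the text points two ways. Section 10.1.1.1 ties it to the listed reactions: "the following solicited adverse events are non-serious adverse events of interest for this study; they will be collected using vaccine diary". Section 9.2.4 is open-ended: "Parents will be asked to fill down a 42-day vaccine diary to record adverse events including local reaction" and further named reactions. It then has investigators record unsolicited events at visits.

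The schedule in Section 9.1 places paediatrician contact at Visits 1 to 4 and the health record check at Visits 1, 2 and 4. Section 9.2 names paediatrician contact for missing illness data at 9 and 24 months only. All groups receive the second MMR at Visit 3 (Section 9.3.4), and the following visit is Visit 4 at 24 months (Section 9.3.5).

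**The concern.** The plan needs a dated onset within 42 days and a causality judgement for every unsolicited event. For the second dose, however, it schedules no question about such events near that window. The paediatrician contact attached to Visit 3 follows once the family has left, so it cannot pick up reactions to the dose just given. The third vaccine diary is handed out at Visit 3 and reviewed with the parent only at Visit 4.

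A minor event first asked about at 24 months may be forgotten. If remembered, it may lack the onset date needed to pass the 42-day test. At stake is the completeness of the safety outcome after second doses. Section 5.4 defines that outcome as day 0 to day 42 after MMR, without limiting it to the first dose. Any reading of first-dose against second-dose rates is also affected, because the two would be collected with very different delays.

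**Working it through.** The protocol states no interval between the close of the window and the next enquiry, so there is no figure of its own to reproduce. The interval follows from the visit schedule.

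**Inputs.** Visit ages are 6, 9, 12 or 13, and 24 months. Windows are ±2 weeks for Visits 1 to 3 and ±4 weeks for Visit 4 (Section 9.1). The event window is 42 days (Section 9.2.4.1). One month is 365.25/12 = 30.4375 days.

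**Formula.** Gap = (age at next visit − age at dose) × 30.4375 − 42 days. The range adds and subtracts the two visit windows.

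| Dose | Next visit | Calculation | Gap | Range with windows |
|---|---|---|---|---|
| First, 6 months (M.C., M.M.) | 9 months | 3 × 30.4375 − 42 | 49 days = 7.0 weeks | 3.0 to 11.0 weeks |
| First, 9 months (C.C.) | 12 months | 3 × 30.4375 − 42 | 49 days = 7.0 weeks | 3.0 to 11.0 weeks |
| First, 9 months (C.M.) | 13 months | 4 × 30.4375 − 42 | 80 days = 11.4 weeks | 7.4 to 15.4 weeks |
| Second, 12 months (M.C., C.C.) | 24 months | 12 × 30.4375 − 42 | 323 days = 10.6 months | 9.2 to 12.0 months |
| Second, 13 months (M.M., C.M.) | 24 months | 11 × 30.4375 − 42 | 293 days = 9.6 months | 8.2 to 11.0 months |

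The second-dose gap is about 6 to 6.6 times the early first-dose gap (293/49 and 323/49).

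**How many doses.** Each of 500 children is due two MMR doses. So 500 of 1,000 planned doses are second doses.

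**What else runs between Visits 3 and 4.**

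- Serious events are collected throughout (Section 10.1).
- Solicited reactions go into the 42-day diary, entered online by the parent (Sections 9.3.4 and 12.1.1).
- Infections, allergic disease and medically attended trauma are asked about in parent questionnaires at least monthly, with dates (Section 9.2, Table 4).
- Any other non-serious event has no scheduled route before Visit 4. It depends on the parent phoning in, or on the diary if it accepts such entries.

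**Is the last category empty?** No. The label data reproduced in Section 3.4.1.2.1.1 list lymphadenopathy, anorexia and insomnia, each at 0.1% to 1%. None is on the solicited list or in the questionnaire categories. If those frequencies applied, 500 second doses would give 500 × 0.001 = 0.5 to 500 × 0.01 = 5 events of each kind.

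**The case against.** A reader might infer that unsolicited events are sought only at visits. The protocol does not say that. It also names spontaneous parent contact, and Section 9.3.2 gives every family a card with a number to call if an adverse event occurs. Questionnaires continue until 24 months. The label's respiratory infection, otitis and bronchitis are therefore dated as they happen, and serious events never depend on a visit. For medically attended events, the paediatrician's record fixes the date, and reviewing it late does not spoil it. The diary wording in Section 9.2.4 may already admit other events. The case report form and the Safety Reporting SOP, which could settle this, are not shown. Finally, this is a Category A trial of a licensed vaccine that deliberately limits what it records.

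Most of this stands, and it narrows the point to non-serious events that are neither solicited, infectious, allergic nor medically attended trauma. It does not remove the point. Spontaneous contact is passive. The questionnaires are not described as a safety source. The two sections that govern unsolicited events do not name the diary. And Section 9.2.4.1 asks for all unsolicited events through day 42, whatever the risk category.

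**Conclusion.** The point holds in a limited form. After the second MMR, the first scheduled enquiry about unsolicited events comes about 9.6 to 10.6 months after the window closes, and at least 8.2 months allowing for visit windows. For the early first dose it comes after about 7 weeks. The consequence is probable under-recording of a small class of minor events after second doses, and a first- versus second-dose comparison that partly reflects the timing of the question. The documents give no capture rates, so the shortfall cannot be put as a percentage. The conclusion assumes nominal visit ages and a diary confined to solicited events, a point on which Sections 9.2.4 and 10.1.1.1 disagree.

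Two stronger readings should be resisted.

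- **Bias in AIM10.** A reader might infer that the safety aim is biased. It concerns early first vaccination (Section 4.4), where the gaps are 49 days against 49 or 80 days. The second-dose delay is similar in all four groups. With Visit 3 held as planned, that contrast is not materially affected.
- **Delegation of Visit 3.** A reader might infer a much longer gap for the 9-month dose from the footnote "If funding is insufficient, V3 might be simplified and delegated to the treating paediatrician". Section 6.1.5 passes the tasks to the treating paediatrician, who is a named source of unsolicited events. Nothing says that the event review would be dropped.

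The change is worth making because a collection rule cannot be repaired at analysis.

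**What to change.** Reconcile Sections 9.2.4, 9.2.4.1.3, 10.1.1.1 and 10.1.1.1.3 so that all four state that the vaccine diary takes unsolicited events. Add to each 42-day online diary, in all groups, one open item on any other illness or medical contact since vaccination, with its onset date, to be completed by day 42. Use the visit, paediatrician and record reviews to confirm and complete these entries, and keep spontaneous contact as a further route.

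The cost is one item in an existing REDCap form and a little more coding of minor events. No visit or contact is added.
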